
Dose finding Part: A rolling 6 design will be used to determine the MTD. The MTD will be assessed by DLT as described in [Table 4.1.4.1:2](#). The MTD will be determined as the highest dose at which no more than 1/6 patients experienced DLT. The rolling 6 design was chosen to limit the waiting period for paediatric patients seeking treatment, as depicted below.

MTD expansion cohorts/Phase II part will recruit a minimum of 5 patients in each of the four disease specific cohorts for HGG, DIPG, EM and other solid tumours fulfilling ErbB biomarker selection criteria (see [Section 3.3.2](#)) and an exploratory cohort of patients with proven genomic, transcriptomic or proteomic ErbB alterations. Efficacy will be assessed by objective response (OR) and the OR rate must be considered meaningful by experts in the field of paediatric oncology and regulatory agencies to pursue further clinical development.

Proprietary confidential information.

© 2017 Boehringer Ingelheim International GmbH or one or more of its affiliated companies. All rights reserved.

This document may not - in full or in part - be passed on, reproduced, published or otherwise used without prior written permission.

Tumour material from all patients entered into this clinical trial must be available for retrospective testing of an ErbB pathway deregulation (for DIPG in dose finding part, see [section 3.3.2](#)) or prospective patient screening into the MTD expansion cohorts/Phase II part.

Intra-patient dose escalation: No clear exposure-efficacy correlation for afatinib has been identified in adult cancer patients yet. Conventional dosing in oncology trials is based on the MTD, or a recommended Phase II dose close to the MTD, dependent on overall safety. Treatment at lower dose tiers may be hampered by a presumed lack of efficacy. Assessment of the MTD or the recommended Phase II dose in oncology trials is based on a frequency of patients with DLTs. Trial 1200.120 will allow intra-patient dose escalation. As soon as the next higher dose tier is considered safe by standard DLT incidences in course one, patients of the lower dose tier, who benefit from treatment may resume treatment at the next higher dose. Although these patients will not be counted into MTD dose cohorts – see rolling 6 design- the safety database at the MTD level/ higher dose tiers and hopefully patients' benefit from participation in Phase I dose finding will be increased.

This part has been completed ([c09990672-01](#)).

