The dose finding part has been completed and the MTD was determined at 80% of the approved adult dose (estimated by allometric scaling based on BSA) ([c09990672-01](#)).

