Note that the Rolling 6 design allows enrolling up to 6 patients on each dose cohort. The first cohort of patients will start with dose level 0 (i.e. 80% of adult dose) as listed in [Table 4.1.3:1](#). As soon as at least two patients are treated at dose level 0, the dose level for the third and subsequent patients will be determined based on the number of patients determined to have experienced DLT, those determined without DLT, and those with DLT data pending for the first treatment course, as illustrated in the first row of [Table 4.1.4.1:1](#). For illustration purpose, an example (considering 4 patients treated on dose level 0) is given below:

- 1) If DLT data of all 4 patients are available and none of them observed with DLT, the dose level may be escalated and the 5th patient will be enrolled to dose level 1
- 2) If data is not yet available for one or more of the first 4 patients, or if one patient with DLT is observed, then the 5th patient will remain on dose level 0; the decision on further dose escalation or de-escalation will be made based on the rules illustrated for a 5-patient cohort
- 3) If more than 2 patients are observed with DLTs, the dose will be de-escalated and the 5th patient will be enrolled to dose level -1

If scenario 1) occurs, dose level 1 becomes dose 'd' in [Table 4.1.4.1:1](#). The process repeats after two patients are enrolled on dose level 1.

If scenario 3) occurs, dose level 0 exceeds the MTD, and dose level -1 is the lowest dose level allowed in this trial. Up to six patients will then be treated on this level, if $\leq 1/6$ patients with DLT, then dose level -1 will be the MTD; if ≥ 2 patients with DLT, then there will be no MTD.

Similarly, suppose the trial has been escalated to higher dose levels, e.g. dose level 3, and ≥ 2 patients had DLT, and if dose level 2 treated less than 6 patients previously, then the dose will be de-escalated to level 2 to fill up to 6 patients and the decision will be made according to the last column in [Table 4.1.4.1:1](#).

As shown in [Table 4.1.4.1:1](#), in order for a dose level to be the MTD, there must have been 6 patients treated on the dose level (at most one patient can have DLT) and the next higher dose level exceeded MTD (≥ 2 patients with DLT). The exception to this rule is if none of the 4 dose levels exceeds MTD, then dose level 3 will be MTD.

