4.1.4.3 Dose reduction of afatinib

Treatment related toxicities will be managed by treatment interruptions and subsequent dose reductions of afatinib according to the schedule described in [Table 4.1.4.3: 1](#). Dose reductions will apply to individual patients only. Once the treatment dose has been reduced, it cannot be increased later.

To prevent the development of more severe adverse events, treatment related diarrhoea, nausea and vomiting or rash should be managed early and proactively as described in [Section 4.2](#).

Proprietary confidential information.

© 2017 Boehringer Ingelheim International GmbH or one or more of its affiliated companies. All rights reserved.

This document may not - in full or in part - be passed on, reproduced, published or otherwise used without prior written permission.

Table 4.1.4.3:1 Dose reduction scheme for afatinib

AE type and CTCAE Grade	Action	Dose reduction scheme

Events related to study drug:
 
 • Diarrhoea Grade 2 persisting for 7 or more consecutive days despite adequate anti-diarrhoeal medication/hydration • Reduced renal function to \geq Grade 2 as measured by serum creatinine, proteinuria or decrease in glomerular filtration rate of more than 50% from baseline • Any drug related AE Grade \geq3 	
Pause treatment until patient has recovered to Grade \leq1 or baseline¹.
 
Resume treatment at reduced dose according to schedule opposite.
 
If patient has not recovered to Grade \leq1 or baseline¹ within 14 days, study treatment must be permanently discontinued².
	
If patient was treated at dose level 3, resume treatment at dose level 2
 
If patient was treated at dose level 2, resume treatment at dose level 1
 
If patient was treated at dose level 1, resume treatment at dose level 0
 
If patient was treated at dose level 0, resume treatment at dose level -1
 
If patient was treated at dose level -1, discontinue afatinib.

Acute onset and/or unexplained worsening of pulmonary symptoms (dyspnoea requiring supplementation of oxygen with cough and/or fever)
	
Pause afatinib while clinical assessment to exclude ILD is completed.
	
If ILD is ruled out as a cause of symptoms, grade symptoms and relatedness and report as AEs. If AEs are not related, resume afatinib at current dose.
 
If ILD is confirmed, discontinue afatinib.

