7.3.3 Safety analyses

DLTs will be tabulated for each dose cohort in the Phase I dose finding part. The tabulation will be done in two ways: (1) DLTs with onset in the first treatment course; (2) all DLTs regardless of treatment course at onset. The definition of DLT is defined in [Table 4.1.4.1:2](#).

Events that started within the course of treatment, starting after the first administration of the treatment and until 28 days after the last administration of treatment will be considered as having occurred on treatment. In general later events will be attributed to the post-study period and will be presented separately. However post-study events will be examined to determine whether they need to be combined with on-treatment events in an additional table.

Adverse events will be graded according to CTCAE v3.0 and reported according to BI standards. Serious adverse events will be tabulated. In addition, events leading to dose reduction or treatment discontinuation will be examined, but may not be reported as individual tables, depending upon the extent of overlap.

Descriptive statistics will be used to describe changes in laboratory parameters over time. In addition, all abnormalities of potential clinical significance will be reported. In general, potential clinical significance is defined as at least CTCAE Grade 2 and an increase in

Proprietary confidential information.

© 2017 Boehringer Ingelheim International GmbH or one or more of its affiliated companies. All rights reserved.

This document may not - in full or in part - be passed on, reproduced, published or otherwise used without prior written permission.

CTCAE classification from baseline. The incidence and intensity of adverse events will be correlated descriptively with pharmacokinetic data if possible.

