7.4 PRIMARY ENDPOINT(S)

7.4.1 Dose Finding Part:

One of the primary objectives is to assess the MTD based on the number of patients presenting DLTs during the MTD evaluation period. Therefore, an overall summary of DLTs (see CTP Section 4, Table 4.1.4.1.2 for the definition of DLTs) which occurred during the MTD evaluation period will be provided for each dose cohort from the dose finding cohort treated set. Patients who were replaced within the MTD evaluation period will be excluded from the determination of the MTD but will be considered for all other safety evaluations.

A summary of the number of patients with DLTs overall in any course will be also given by initial treatment and displayed in a similar format to the summary of DLTs occurring in the MTD evaluation period.

The determination of the MTD is based on a Rolling 6 design as illustrated in Section 4, Table 4.1.4.1:1 of the CTP. The MTD is defined as the highest dose at which no more than 1/6 patients experienced DLT considered related to afatinib during the MTD evaluation period. Refer to CTP 7.3.1 for further details on MTD evaluation.

Analysis of the standard PK endpoints is performed according to (2) and (8) as outlined in Section 7.3.5 of the CTP.

7.4.2 MTD expansion cohort part:

Objective response (OR) is defined as a best overall response of complete response (CR) or partial response (PR) based on investigator's assessment according to the institutional

response evaluation criteria for the given tumour type. If the International Criteria for Neuroblastoma Response Criteria (INRC) is used, OR is defined as complete response (CR), very good partial response (VGPR), partial response (PR) and mixed response (MxR). For further details on OR, please refer to CTP Section 7.3.1. The objective response rate will be calculated and reported as proportion of responders with 95% Clopper-Pearson CIs based on all treated patients. Objective response will be summarized regardless of confirmation.

Additional summary or listing may be provided for confirmed response. If only few patients (fewer than 5) achieved objective response, a detailed listing will be reported.

For objective responses, evaluated by institutional response evaluation criteria other than INRC, below confirmation rule for best overall response will be considered.

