7.7 EXTENT OF EXPOSURE

Treatment exposure will be primarily summarized by the total on-treatment time and has been defined in [Section 5.4](#) of this TSAP.

Treatment interruptions before permanent discontinuation will not be excluded. Summary statistics for treatment time by each dose level of afatinib over time will also be provided.

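### The all-course DLT summary is grouped only by starting dose, so a later DLT at the MTD in a patient reduced from level 1 is missing from the level 0 row

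*SAP*

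**What the plan says.** SAP 7.4.1 plans two DLT summaries for the dose finding part. One covers the MTD evaluation period by dose cohort. For the other: "A summary of the number of patients with DLTs overall in any course will be also given by initial treatment". The unit is the patient, not the event. Protocol 7.3.3 has the same structure: "DLTs will be tabulated for each dose cohort in the Phase I dose finding part", once for first-course onset and once for "all DLTs regardless of treatment course at onset".

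Patients need not stay at their starting dose. Protocol 4.1.4.1 allows treatment to continue at a lower dose after a DLT, and Table 4.1.4.3:1 says: "If patient was treated at dose level 1, resume treatment at dose level 0". Protocol 4.1.4.2 allows escalation to the next tier once that tier is considered safe.

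On the level that matters most, Protocol 4.1.3 reports that "the MTD was determined at 80% of the approved adult dose", which is level 0.

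SAP 7.7 organises exposure by dose received: "Summary statistics for treatment time by each dose level of afatinib over time will also be provided".

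**The concern.** The common step-down from level 1 ends at the dose carried into the expansion part. Toxicity at that dose in reduced patients bears on level 0, yet the only DLT summary with a stated grouping beyond course 1 files those patients under level 1.

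This fits poorly with three other places. Protocol 3.2 says that data after intra-patient escalation enlarge "the safety database at the MTD level/ higher dose tiers", which presupposes attribution to the dose received. Protocol 5.2.1 says that DLTs are followed throughout the trial and that all safety data serve to confirm the recommended Phase II dose. SAP 7.7 splits treatment time by actual dose level, so the DLT numerator and the exposure denominator follow different rules and cannot be combined into a rate per level.

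At stake is what the report can say about later-course tolerability at level 0 from the dose-finding patients.

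**Working it through.** Neither document gives a figure for this table, so there is none to reproduce. The check traces the rule and then sizes it.

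**Inputs from the documents**
- Grouping by initial treatment, counting patients: SAP 7.4.1.
- MTD = level 0: Protocol 4.1.3 and Table 4.1.4:1.
- For a level to be the MTD, 6 patients must have been treated there, at most one with a DLT, and "the next higher dose level exceeded MTD", meaning at least 2 patients with DLT: Protocol 4.1.4.1.
- 17 dose-finding patients: Protocol 3.3 and 7.6.

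**Not in the documents:** the split of the 17 by level, how many continued after reduction, how many had later DLTs, and whether anyone was escalated.

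**1. Step-down, traced.** A patient starts at level 1, has a DLT, resumes at level 0 and has another DLT there. By initial treatment the patient already counts once under level 1. The second DLT changes neither row. If the reduction had a non-DLT reason (for example persistent grade 2 rash, Table 4.2.2.2:2), the later DLT at level 0 would be the patient's first and would raise level 1.

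**2. Minimum number open to this.** At least 2 level 1 patients had a DLT: 2/17 = 11.8%. This counts patients who could be affected, not patients known to be.

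**3. Effect on the level 0 row.** Let x be the patients who started at level 0 and had a DLT there, k the patients reduced to level 0, and j those among the k with a DLT at level 0.
- By initial dose: x/6.
- By dose at onset: (x + j)/(6 + k).

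With k = 2 (assumed):

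| x | j | By initial dose | By dose at onset | Difference (points) |
|---|---|---|---|---|
| 0 | 0 | 0/6 = 0% | 0/8 = 0% | 0 |
| 0 | 1 | 0/6 = 0% | 1/8 = 12.5% | +12.5 |
| 0 | 2 | 0/6 = 0% | 2/8 = 25.0% | +25.0 |
| 1 | 0 | 1/6 = 16.7% | 1/8 = 12.5% | -4.2 |
| 1 | 1 | 1/6 = 16.7% | 2/8 = 25.0% | +8.3 |
| 1 | 2 | 1/6 = 16.7% | 3/8 = 37.5% | +20.8 |

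With k = 4 and x = 1, the by-onset figure runs from 1/10 = 10% (j = 0) to 5/10 = 50% (j = 4). The planned table shows 16.7% throughout. The limit of one DLT at level 0 applies to course 1, so an all-course x could be higher.

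**4. Escalation.** If one level 0 patient is escalated and has a first DLT at level 1, level 0 by initial dose goes from 1/6 = 16.7% to 2/6 = 33.3%. By dose at onset it stays at 16.7%.

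**5. Could escalation have happened?** Level 1 finally failed, so escalation to it was open only if it was first considered safe and failed later. Table 4.1.4.1:1 permits that path. Without it, at most 6 + 6 = 12 evaluable patients fill levels 0 and 1. The total of 17 does not settle the matter, because it counts patients entered and the table ignores unevaluable ones.

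**The case against.** The strongest defence is that the SAP does what the protocol prescribes. Protocol 7.3.3 calls for tabulation by dose cohort whatever the course, and display by assigned cohort is a legitimate convention. That stands: the planned table is not an error and should stay.

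The weight of the data is also limited. The MTD rests on the first 28 days (SAP 5.1). Confirming the recommended dose is assigned mainly to the expansion cohorts (Protocol 3.1 and 7.6), with up to 38 evaluable patients. That stands too.

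Other SAP outputs may help. SAP 7.8.1 tabulates DLTs for all courses by treatment and adds listings for events of special interest, which include DLTs. This is only partial relief: treatment is not defined there as initial dose or dose at onset, the listings do not name dose at onset, and SAP 6.1 defines one on-treatment period not divided by dose. So it cannot be said that these DLTs are absent under level 0 everywhere in the SAP, only that no table is specified to show them there.

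Finally, a by-onset table has its own bias. Reduced patients are selected for prior intolerance, and one patient can appear at several levels. That is a reason to label it carefully, not to omit it.

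**Conclusion.** A minor gap in a descriptive safety display. The grouping rule and the step-down route are stated in the documents. The size depends on how many patients resumed at level 0 and had a further DLT, which is not stated. With 6 patients at level 0, 2 step-downs and one further DLT, the difference is 8.3 or 12.5 points.

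A reader might infer more in four ways, none supported:
- **That the MTD or recommended dose is wrong.** The MTD uses first-course DLTs only.
- **That events at level 0 are added to level 1.** Patients are counted, so a reduced patient with a prior DLT adds nothing further to level 1.
- **That each misplaced event shifts level 0 by 1/6, or 16.7 points.** This keeps the denominator at 6. It fits the escalation case, but step-downs also enlarge the level 0 denominator.
- **That DLTs after escalation were in fact counted under level 0.** The documents do not say that any patient was escalated from level 0.

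**What to change.** 1. In SAP 7.4.1, keep the by-initial-dose summary. Add an all-course DLT table by dose level at onset, and do the same for the main dose-finding AE table.
2. Give two denominators per level: patients ever treated at that level, and treatment time at that level as already planned in SAP 7.7.
3. In SAP 7.8.1, state whether treatment in the DLT and AE tables means initial dose or dose at onset.
4. Label the new display descriptive, noting that patients may appear at more than one level and that reduced patients are selected for prior intolerance.

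The cost is one added version of each of these tables. Dose at onset can be derived from the dosing records, and no new data are needed.

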7.5 SECONDARY ENDPOINT(S)

7.5.1 Key secondary endpoint(s)

This section is not applicable as no key secondary endpoint has been specified in the protocol.

7.5.2 (Other) Secondary endpoint(s)

For progression free survival (PFS), objective response (OR) and duration of objective response (DoR), a descriptive and graphical summary of the endpoint will be provided. The Kaplan-Meier estimates of PFS and DoR (if applicable) and 95% confidence intervals will be calculated at the time of each planned assessment. For the dose finding part, the number of patients with OR will be summarized by dose level. If fewer than 5 patients achieved OR, then DoR will only be listed; Kaplan-Meier estimates will not be calculated and no summary table or graph will be provided.

To evaluate the potential influence of age on pharmacokinetic parameters like C_{max} and AUC, an exploratory subgroup analysis will be performed for different age groups. For this, binning of age into groups will be performed to ensure that groups have reasonable patient numbers. If feasible, a correlation of age and PK parameters may be performed.

7.7 EXTENT OF EXPOSURE

Treatment exposure will be primarily summarized by the total on-treatment time and has been defined in [Section 5.4](#) of this TSAP.

Treatment interruptions before permanent discontinuation will not be excluded. Summary statistics for treatment time by each dose level of afatinib over time will also be provided.

7.8 SAFETY ANALYSIS

All safety analyses will be performed on the treated set.

7.8.1 Adverse events

The analyses of adverse events (AE) will be descriptive in nature. All analyses of AEs will be based on the number of patients with AEs and not on the number of AEs. For analysis of duration, severity etc. of multiple AE occurrences, data on the case report form (CRF) will be collapsed into AE episodes provided that all of the following applies:

- The same MedDRA lowest level term was reported for the occurrences.
- The occurrences were time-overlapping or time-adjacent (time-adjacency of two occurrences is given if the second occurrence started on the same day or on the day after the end of the first occurrence).
- Treatment did not change between the onset of the occurrences or treatment changed between the onsets of the occurrences, but no deterioration was observed for the later occurrence.

For further details on summarization of AE data, please refer to the BI guideline (4).

The analyses of adverse events will be based on the concept of treatment-emergent adverse events. That means that all adverse events occurring between first drug intake and 28 days after last drug intake or death, whichever occurs first, will be assigned to the on-treatment period. All adverse events occurring before any study drug intake will be assigned to 'screening' and all adverse events occurring after last study drug intake + 28 days will be assigned to 'Off-treatment' (for listings only). For details on the treatment definition, see [Section 6.1](#).

An overall summary of adverse events will be presented. The frequency of patients with adverse events will be summarised by highest CTC grade (grades 1, 2, 3, 4, 5 and all grades), treatment, primary system organ class and preferred term for each of the following AE tables as well as relatedness of AEs to treatment and seriousness:

- DLTs (1st course and all courses)
- All AEs
- Drug-related AEs
- AEs leading to dose reduction
- AEs leading to treatment discontinuation
- Drug-related AEs leading to dose reduction
- Drug-related AEs leading to treatment discontinuation
- AEs leading to death
- Serious AEs
- Drug related serious AEs
- Other significant AEs, defined as AEs leading to dose reduction or permanent discontinuation of study medication
- Non-serious AEs with higher than 5% occurrence rate for disclosure on ClinicalTrials.gov

Please refer to CTP Section 5.2.2.1 for definitions of the adverse events. All tables will be sorted by system organ classes (SOC) according to the standard sort order specified by the European Medicines Agency (EMA). Preferred terms (PTs) will be sorted by frequency (within SOC).

The table for all AEs will be repeated with the project defined grouping of AE terms (acute renal failure associated with severe diarrhoea, acne, rash, stomatitis, conjunctivitis, paronychia, severe cutaneous adverse reactions, interstitial lung disease, keratitis, hepatic impairment, pancreatitis, heart failure, gastrointestinal perforation, hypersensitivity reactions, nail disorders and fatigue). Details of the project defined groupings will be defined in the technical TSAP. In these tables the grouped AEs will replace the original PTs for all AEs that are included within the grouped term. The grouped AE categories will then be tabulated along with all remaining MedDRA PTs, sorted by descending frequency.

A reference table presenting the entire project defined groupings and MedDRA PTs within each grouping will also be produced.

Additional AE tables will be produced for AEs of special interest (hepatic injury as defined in CTP Section 5.2.2.1 and dose limiting toxicities as defined by CTP Section 4, table 4.1.4.2). Listings providing further details on highest CTC grade, action taken with study drug and time to first onset of AE will be produced.

